7.2 Secondary Efficacy Endpoints

- 1) Proportion of constipated patients who use/do not use other constipation treatment methods during treatment and after the vibrating capsule treatment and at the end of follow-up;
- 2) Proportion of patients with an average increase of ≥ 1 CSBMs per week compared to the baseline period;
- 3) Proportion of respondents with an average of ≥ 3 SBMs per week during the treatment period;
- 4) Proportion of subjects with ≥ 3 SBMs per week and an increase of ≥ 1 CSBMs during at least 4 weeks of treatment compared to baseline;
- 5) Proportion of patients with an average increase of ≥ 1 CSBMs per week during the follow-up phase compared to the baseline period;
- 6) Proportion of patients with an average of ≥ 3 SBMs per week during the follow-up phase;
- 7) Proportion of patients with a reduction of ≥ 1 point in total PAC-QOL and PAC-SYM scores after treatment compared to the baseline period;
- 8) Proportion of patients with a reduction of ≥ 1 point in total PAC-QOL and PAC-SYM scores after follow-up compared to the baseline period;
- 9) Time of first use of laxative or enema after a course of vibrating capsule treatment (6 weeks);
- 10) Proportion of constipated patients (including different constipation types, occupations, age groups, BMI, gender, and baseline treatment status) responding to vibrating capsule treatment and at the end of follow-up.

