3.1 Purpose of the Clinical Trial

Through this real-world study, to analyze the response of functional constipation patients with different severity, treatment status, capsule dosage, and combined medication to Vibrabot capsule, as well as the duration of efficacy maintenance during the follow-up period; to compare the efficacy with patients treated with drugs or other therapies during the same period, explore the possibility of curing functional constipation patients, further improve the treatment satisfaction of constipation patients, and promote the establishment and application of consensus or guidelines for the use of Vibrabot capsule in treating functional constipation.

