7.1.2 Visit Content

Each patient will undergo a series of study visits, including screening, treatment visit, and follow-up visit. The visit process is briefly described as follows:

Visit 1 (0 ~ 1 day) - Baseline/Screening Period:

This visit includes:

The patient will sign an informed consent form;

Set the inclusion/exclusion criteria;

Guide patients to fill out the questionnaire using the Official Account and complete the *Baseline Period Questionnaire* in the Official Account.

Prescription Vibrabot capsule treatment or other treatment options.

Visit 2 (Week 2 ±3 days) - Treatment Period 1:

This visit includes:

Fill out the *Daily Bowel Movement Questionnaire* in the WeChat Official Account every day, take Vibrabot capsules on time or opt for other treatment plans;

Fill out the *Constipation Symptom Self-Assessment Scale and Assessment Scale for Quality of Life with Constipation* in the Official Account every 2 treatment weeks.

Record adverse events and concomitant treatments;

Prescription Vibrabot capsules or other treatment options.

Visit 3 (Week 4±3 days) - Treatment Period 2

This visit includes:

Fill out the *Daily Bowel Movement Questionnaire* in the WeChat Official Account every day, take Vibrabot capsules on time or opt for other treatment plans;

Fill out the *Constipation Symptom Self-Assessment Scale and Assessment Scale for Quality of Life with Constipation* in the Official Account every 2 treatment weeks.

Record adverse events and concomitant treatments;

Prescription Vibrabot capsules or other treatment options.

Visit 4 (Week 6 ±3 days) - Treatment Period 3

This visit includes:

Fill out the *Daily Bowel Movement Questionnaire* in the WeChat Official Account every day, take Vibrabot capsules on time or opt for other treatment plans;

Fill out the *Constipation Symptom Self-Assessment Scale and Assessment Scale for Quality of Life with Constipation* in the Official Account every 2 treatment weeks.

Record adverse events and concomitant treatments.

Visit 5 (Week 10±3 days) - Follow-up Period:

This visit includes:

Fill out the *Daily Bowel Movement Questionnaire* in the WeChat Official Account every day;

Fill out the *Constipation Symptom Self-Assessment Scale and Assessment Scale for Quality of Life with Constipation* in the Official Account every 2 treatment weeks;

Record adverse events and concomitant treatments.

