8.1 Statistical Analysis of the Population

Sample Size Calculation

H0: The effectiveness rate of vibrating capsule treatment for constipation $\leq 50\%$

H1: The effectiveness rate of vibrating capsule treatment for constipation $> 50\%$

In a single-group design, if the study goal is to evaluate the effectiveness of vibrating capsule

treatment for constipation and compare it with the expected 50% effectiveness rate, then a one-sample proportion test can be considered for sample size calculation.

Sample size calculation formula for single sample proportion test is:

$$n = \frac{\left[Z_{1-\alpha} \sqrt{P_0(1-P_0)} + Z_{\beta} \sqrt{P_T(1-P_T)} \right]^2}{(P_T - P_0)^2}$$

Where:

- (1) p is the overall expected success rate (here it is estimated that the effectiveness of treating constipation with vibrating capsules is 50%);
- (2) p_0 is the success rate under the null hypothesis (assuming a 40% success rate under the null hypothesis);
- (3) The probability of Type I error α is set to 0.05, and the probability of Type II error β is set to 0.2 (i.e., the statistical power is $1-\beta=0.8$);

At least 191 participants are needed for this study. Assuming a 20% loss to follow-up, the final sample size required is 239. Considering this is a real-world study and taking into account the outpatient volume of the participating center, it is planned to enroll 300 patients who will take vibrating capsules for 6 weeks, and at the same time, include ≥ 300 patients undergoing constipation treatment during the same period.

(1) Full Analysis Set (FAS) is the set of patients that is as close as possible to the ideal implied by the Intention-to-Treat principle. Specifically, in this trial, the FAS is the data set of all patients with baseline evaluation who take at least one capsule treatment/other treatment option. Missing data for primary efficacy endpoints in the FAS will be imputed according to certain rules while missing data for secondary efficacy endpoints will not be imputed.

(2) Per Protocol Set (PPS) is a subset of the FAS and refers to the set of subjects who meet the inclusion criteria, do not meet the exclusion criteria, complete the treatment, and have no protocol violations. Specifically, in this trial, the PPS includes the patients in the FAS who:

- a) complete the full treatment,
- b) meet the inclusion criteria and do not meet the exclusion criteria,
- c) have good compliance with capsule administration/other treatment, and

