8.2 Statistical Analysis Principle

SAS (version 9.2 or above) or R is used in this study for statistical analysis.

Measurement data are presented as the number of cases, mean±standard deviation, median, minimum, maximum, and quartiles. Count data are presented as frequencies and percentages. Parametric methods are first considered for statistical tests, and non-parametric methods are used if the data distribution differs significantly from the distribution assumed by the statistical test.

A two-sided hypothesis test is used for difference test, and the alpha level is set to 0.05 (two-sided); that is, if the p-value is <0.05, the difference is considered statistically significant.

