8.3 Statistical Procedure for all Data

The investigators should submit completed case report forms to the CRA in a timely manner. The CRA should check the case report forms, verify the original records, and check for any omissions or errors. After ensuring there are no errors, the CRA should deliver the forms to the principal investigator. If there are any questions about the case report forms, the CRA should ask the investigators, who should respond promptly and make any necessary data modifications and confirmations.

Do not fill in missing data.

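### Secondary endpoint 9 (time to first laxative or enema) is censored at about four weeks, but the plan gives it no time-to-event method or censoring rule; taken literally, its general rules would summarise only patients who relapsed

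*Combined protocol and SAP*

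**What the plan says.** Section 7.2 Secondary Efficacy Endpoints, item 9, reads "Time of first use of laxative or enema after a course of vibrating capsule treatment (6 weeks". Section 7.1.2 fixes the observation period: treatment ends at "Visit 4 (Week 6 ±3 days) - Treatment Period 3" and the last contact is "Visit 5 (Week 10±3 days) - Follow-up Period". Section 3.1 gives the aim that the endpoint serves: the study is to analyse response "as well as the duration of efficacy maintenance during the follow-up period".

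No section gives a method specific to this endpoint. Kaplan-Meier, log-rank, Cox and censoring appear nowhere. What remains is general:

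- Section 8.2, on description: "Measurement data are presented as the number of cases, mean±standard deviation, median, minimum, maximum, and quartiles".
- Section 8.2, on testing: "Parametric methods are first considered for statistical tests, and non-parametric methods are used if the data distribution differs significantly".
- Section 8.1, on the full analysis set: "missing data for secondary efficacy endpoints will not be imputed".
- Section 8.3: "Do not fill in missing data".

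**The concern.** A time to first use exists only for patients who use a laxative or enema before observation stops. For the others, all that is known is that the time exceeds their follow-up. A mean, median and quartiles need one number per patient, and the plan does not say what number, if any, an event-free patient receives. With nothing to enter and an instruction not to fill gaps, an analyst following the text would leave the field empty, and the summary would run on users only.

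The patients lost in this way are those with the best outcome. Endpoint 9 is the only one of the ten secondary endpoints expressed as a time, and duration of benefit is a stated aim. A short users-only mean could be read as a short-lived effect in a cohort where most patients never needed a laxative.

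**Working it through.** The plan gives no figure for endpoint 9, so there is none to reproduce. Its sample size concerns the primary endpoint and does not bear on this point.

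**Inputs from the documents.** The window runs from Week 6 to Week 10, so T = 4 × 7 = 28 days. With ±3 days at each visit it ranges from 28 − 6 = 22 to 28 + 6 = 34 days. The planned capsule cohort is 300 (8.1).

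**Assumptions, not in the documents.** The laxative-free share s at day 28 is varied. The hazard λ is constant. Dropout is ignored, although 8.1 allows for 20% loss to follow-up, which would add earlier censoring.

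**Formulas.**

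- Hazard: λ = −ln(s)/28.
- Users-only mean: E[T | T < 28] = 1/λ − 28·s/(1 − s).
- Mean laxative-free time within the window over all patients (restricted mean): (1 − s)·E[T | T < 28] + 28·s.

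Worked for s = 0.50: λ = 0.6931/28 = 0.02476 per day and 1/λ = 40.4. The users-only mean is 40.4 − 28 = 12.4 days. The restricted mean is 0.5 × 12.4 + 28 × 0.5 = 20.2 days.

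| Laxative-free share s | Patients of 300 with no time value | Users-only mean (days) | Restricted mean, all patients (days) |
|---|---|---|---|
| 30% | 90 | 11.3 | 16.3 |
| 50% | 150 | 12.4 | 20.2 |
| 70% | 210 | 13.2 | 23.6 |
| 85% | 255 | 13.6 | 25.8 |

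Across the table the users-only mean moves a little over two days, and the restricted mean more than nine.

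**Ceiling.** As λ approaches zero, event times within the window become uniform, so the users-only mean tends to 28/2 = 14 days and cannot exceed it under a constant hazard, however durable the effect.

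**Median against median.** At s = 50% the users-only median is 11.6 days and the Kaplan-Meier median is 28.0. At s = 60% they are 12.2 days and not reached.

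**Window sensitivity.** As the share of users falls from 90% to 10%, the users-only mean runs from 9.0 to 13.8 days for T = 28, from 7.1 to 10.8 for T = 22, and from 11.0 to 16.7 for T = 34. The pattern is the same.

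**What does not depend on the hazard.** The restricted-mean identity holds for any hazard. A users-only summary discards the term 28·s, which is the contribution of the event-free patients, so it always understates laxative-free time when s is above zero.

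**The case against.** The strongest reply is that this is silence rather than an error. No section says that event-free patients are excluded or that a mean will be computed for endpoint 9. A reader might infer that the plan states a wrong rule; it does not. The exclusion follows from general rules applied to an endpoint they do not fit. A patient followed to Week 10 without an event is also observed, not missing, and censoring is not imputation, so neither missing-data rule forbids Kaplan-Meier. Section 8.2 leaves room for non-parametric tests and requires the number of cases, so a reduced denominator would be visible. All of this stands. It does not supply a method: the plan still leaves the value for event-free patients undefined, and its only descriptive rule for quantitative data cannot handle them.

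A reader might also infer that the durability aim is lost. It is not. Endpoint 1 covers use or non-use of other treatments up to the end of follow-up, and endpoints 5, 6 and 8 cover bowel-movement response and symptom and quality-of-life scores in follow-up. They partly capture durability as proportions, but none gives time to first use.

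A further tempting reading is that the endpoint would be blind to durability. That depends on the scenario. In a simulation with 300 per group, constant hazard and 1,000 runs, users-only tests rejected about 76% of the time for 80% versus 40% users, but about 7% for 50% versus 40%, where log-rank reached 72%. Endpoint 9 is worded only for patients after a capsule course, and no between-group test is stated for it, so these figures are illustrative and the point does not rest on them.

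Finally, it should not be assumed that the data needed are already in hand. The contents of the daily questionnaire are not shown. Dated laxative use is plausible, because the definition of a spontaneous bowel movement in section 7 needs medication use in the preceding 24 hours, but it is not documented.

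**Conclusion.** The point holds as a gap with a predictable bad default. Endpoint 9 is right-censored at about four weeks, no time-to-event method or censoring rule is given, and literal use of 8.1, 8.2 and 8.3 would describe only patients who relapsed.

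The direction of the distortion is certain for any users-only summary. Its size rests on the assumed constant hazard, event shares and 28-day window used above. Actual values may differ, and under a rising hazard the 14-day ceiling would not apply.

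This is one of ten secondary endpoints, with no hypothesis or sample size attached, and the primary conclusion is unaffected. It should be corrected because it serves a stated aim and the remedy is cheap.

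**What to change.** In the SAP text:

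1. Exempt endpoint 9 from the mean±SD rule in 8.2 and name it as a time-to-event endpoint.
2. Set time zero at the end of the six-week course. The event is first laxative or enema use; censor at the last completed daily questionnaire or at Visit 5.
3. Present the Kaplan-Meier curve and the laxative- or enema-free proportion at four weeks with a 95% CI. Give the median only if it is reached.
4. Report patients already using a laxative at the end of the course separately, since they have no laxative-free time to measure.
5. State that being event-free is an observed, censored outcome and does not fall under the missing-data rules in 8.1 and 8.3.
6. Confirm that the questionnaire or the concomitant-treatment record captures the date of laxative or enema use.

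The cost is SAP wording and a small amount of analysis. If step 6 shows that dates are not captured, a date field would also be needed.

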7.3 Safety Evaluation Method

The safety is evaluated by the occurrence of device-related adverse events (AEs) and device-related serious adverse events (SAEs) throughout the study period.

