|-------------------------|--|
| | 
week during the follow-up phase compared to the baseline period;
 
6) Proportion of patients with an average of ≥ 3 SBMs per week during the follow-up phase;
 
7) Proportion of patients with a reduction of ≥ 1 point in total PAC-QOL and PAC-SYM scores after treatment compared to the baseline period;
 
8) Proportion of patients with a reduction of ≥ 1 point in total PAC-QOL and PAC-SYM scores after follow-up compared to the baseline period;
 
9) Time of first use of laxative or enema after a course of vibrating capsule treatment (6 weeks);
 
10) Proportion of constipated patients (including different constipation types, occupations, age groups, BMI, gender, and baseline treatment status) responding to vibrating capsule treatment and at the end of follow-up.
 |
| Safety Endpoints | 
 1. The incidence (%) and the number of device-related adverse events (AEs) and serious adverse events (SAEs); 2. The incidence (%) and the number of device defects. |

1. About the Sponsor

| | |
|--------------|---|
| Name: | ANKON Medical Technologies (Shanghai) Co., Ltd. |
| Address: | [name] |
| Contact No.: | [name] |

2. List of All Clinical Trial Sites and Investigators in the Multi-Center Clinical Trial

| Site No. | Clinical Trial Site Name | Principal Investigator | Professional Title |
|----------|---|------------------------|----------------------------|
| 01 | The First Affiliated Hospital of Navy Medical University (Shanghai Changhai Hospital) | [name] | Chief Physician, Professor |

| | | | |
|----|---|----------------|----------------------------|
| 02 | Ruijin Hospital, Shanghai Jiao Tong University School of Medicine | [name] | Chief Physician, Professor |
| 03 | Shanghai Tongji Hospital | [name] | Chief Physician |
| 04 | Shanghai Tenth People's Hospital | [name] | Chief Physician, Professor |
| 05 | Shanghai First People's Hospital | [name] | Chief Physician |
| 06 | Shanghai Sixth People's Hospital | [name] | Chief Physician, Professor |
| 07 | Shanghai Ninth People's Hospital | [name] | Chief Physician |
| 08 | Shanghai Yangpu District Central Hospital | [name] | Chief Physician |
| 09 | Shanghai Pudong New Area Gongli Hospital | [name] | Chief Physician |

3. Purpose and Content of the Clinical Trial

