13.1 Definition of Adverse Events and Reporting Requirements

Definition: An AE is any untoward medical occurrence in a clinical trial, whether or not considered device-related.

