13.1.3 Adverse Event Record

All AEs that occur during the study must be truthfully recorded on the adverse event form. The investigator shall give targeted treatment for the AE and follow up until the symptoms are stable or disappear.

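### Section 7.3 evaluates safety only on device-related events, although all adverse events are recorded for every patient; all-cause incidence by treatment received should be added

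*Combined protocol and SAP*

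**What the plan says.** Section 7.3 is one sentence, which evaluates safety over the whole study by "device-related adverse events (AEs) and device-related serious adverse events (SAEs"). The Safety Endpoints row of the Protocol Summary words the first endpoint differently: "The incidence (%) and the number of device-related adverse events (AEs) and serious adverse events (SAEs"). It adds a second endpoint that section 7.3 does not mention: "The incidence (%) and the number of device defects".

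Collection is wider than evaluation. Section 13.1 states: "An AE is any untoward medical occurrence in a clinical trial, whether or not considered device-related". Section 13.1.3 states: "All AEs that occur during the study must be truthfully recorded on the adverse event form". The visit schedule covers everyone, whichever treatment is prescribed: "Each patient will undergo a series of study visits, including screening, treatment visit, and follow-up visit" (section 7.1.2). The flow chart in section 7.1.1 marks adverse events at all five visits.

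Section 13.1.2 grades relationship on five levels, against the investigational device only, and does not say which grades count as device-related. Under section 3.2, treatment follows patient need, preference and the doctor's judgement, and may be capsule, other treatment or both. Section 3.1 states a between-cohort comparison of efficacy and none of safety. Section 8.1 defines the safety set in terms of randomised patients, although no randomisation is described.

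**The concern.** No endpoint in section 7 and no analysis in section 8 uses the all-cause adverse-event data that the trial collects. What section 7.3 would report is a rate filtered through a causality judgement by investigators who know the treatment.

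That filter matters more than usual here. Section 9.2 names capsule retention as the adverse event of most concern, then says in advance that it is due to the patient's hidden condition and is not caused by the capsule. Section 5.1 presents the product as free of side effects. Section 13.1.2 makes literature support part of the definite and possible grades, which is hard to meet for a product that section 4 calls the first of its kind. The symptoms expected during vibration (bloating, abdominal pain, diarrhoea) may plausibly also come from constipation or its drug treatment, so attribution in a single case is weak.

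At stake is what can be said about harm. The study aims to support a consensus or guidelines (section 3.1). It would set efficacy beside a concurrent cohort while leaving that cohort's adverse events out of the evaluation.

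**Working it through.** The plan states no safety rate, precision target or safety sample size, so there is no safety figure to reproduce. The check is a reading of the text, with illustrations on stated assumptions.

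**1. Collected against evaluated**
- Defined: any untoward event, related or not (13.1).
- Recorded: all of them, for each patient, at every visit (13.1.3, 7.1.1, 7.1.2).
- Evaluated: device-related AEs and device-related SAEs (7.3).

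The unrelated events are collected and then dropped from the evaluation.

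**2. Patients who take no capsule**
Relationship is graded against the capsule only, so a patient who never takes one cannot have a device-related event. In a capsule-free group of n patients the section 7.3 count is 0/n (0/300 at the planned minimum), whatever happens to them.

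**3. Patients who take a capsule**
Let *p* be the proportion with any AE, and *f* the share of those patients with at least one event judged device-related. The reported incidence is *p* × *f*. The values of *p* below are assumptions.
- *p* = 10%: 0%, 5%, 10% for *f* = 0, 0.5, 1.
- *p* = 20%: 0%, 10%, 20%.
- *p* = 30%: 0%, 15%, 30%.

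The all-cause incidence *p* does not depend on *f*. With 300 patients its 95% half-width is 1.96 × √(*p*(1−*p*)/300), which is 3.4, 4.5 and 5.2 points for *p* = 10%, 20% and 30%.

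**4. Retention**
Section 9.2 cites a rate of 0.73% (95% CI 0.59% to 0.89%) without saying whether it is per patient or per capsule. Assume per patient:
- Expected number in 300: 300 × 0.0073 = 2.2 (1.8 to 2.7).
- Chance of at least one: 1 − (1 − 0.0073)^300 = 0.89 (0.83 to 0.93).

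An investigator who applied the causal statement in section 9.2 could grade every such case as unrelated, and the section 7.3 count would be 0.

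**5. What a between-cohort difference could show**
Assume 300 patients per group and all-cause rates of 10% and 6%. The difference is 4 points with half-width 1.96 × √(0.10×0.90/300 + 0.06×0.94/300) = 4.3 points, an interval of −0.3 to 8.3. If both rates are equal, at 5% or at 30%, the half-width is 1.96 × √(2×0.05×0.95/300) = 3.5 or 1.96 × √(2×0.30×0.70/300) = 7.3 points. This is descriptive precision only. Separating combination patients from the 300 would widen it, and the plan gives no split.

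**6. The two SAE wordings**
In the synopsis the qualifier stands once, before AEs; in section 7.3 it is repeated before SAEs. If the single qualifier governs both nouns, the two places agree. If it governs only the first, the synopsis counts all SAEs and section 7.3 does not. The text does not settle which.

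**The case against.** The strongest reply is that this is a post-marketing study of an approved device, and a device-related endpoint fits that scope. The protocol sets out to compare efficacy, not safety, between the cohorts. SAEs also reach the ethics committee whatever their cause (section 13.4.1). That reply stands as far as bias is concerned. It does not explain why all-cause events are collected at every visit and then left out of every named analysis, and expedited reporting does not give an incidence.

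A reader might infer stronger points that the documents do not support:
- *A planned safety comparison is invalidated by a comparator rate of zero.* No such comparison is planned, so the zero makes the endpoint uninformative for capsule-free patients but distorts no stated test. Nor is it zero for everyone: combination therapy is allowed, and the plan does not say in which cohort those patients are counted.
- *The synopsis and section 7.3 contradict each other on SAEs.* The synopsis is ambiguous, and one natural reading matches section 7.3.
- *The whole plan looks only at device-related events.* That is true of section 7.3. The synopsis also lists device defects, and may include all SAEs.
- *The between-cohort difference is the only measure free of attribution.* The all-cause rate in capsule patients alone is equally free of it. The difference is confounded by treatment choice, and for retention there can be no comparator under any wording.

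Open-label assessment is itself inferred from the design: no blinding or independent adjudication is described.

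**Conclusion.** The point holds as an omission in the safety evaluation. Section 7.3 discards all-cause information that the trial already collects, leaves the capsule rate dependent on open-label attribution, and takes no adverse-event information from patients who receive no capsule. The primary efficacy analysis is untouched.

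The size cannot be fixed from the documents, because they give neither an all-cause rate nor a share attributed; the figures above are ranges on assumed rates and group sizes of 300. What does not depend on those assumptions is that the device-related rate cannot exceed the all-cause rate, and that the gap between them is set by judgement.

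Two wording matters need reconciling alongside: which SAEs the synopsis means, and the absence of device defects from section 7.3. The safety set also needs a definition that can be applied, since per-group rates have no valid denominator while it refers to randomised patients.

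**What to change.** Use one wording in the Protocol Summary and in section 7.3:
- Incidence and number of all AEs and all SAEs regardless of relationship, by treatment actually received (capsule alone, combination, other treatment), each incidence with a 95% confidence interval.
- The device-related subset, for patients who took a capsule, with the section 13.1.2 grades that count as device-related stated.
- Incidence and number of device defects, kept as an endpoint.

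Report any between-cohort difference descriptively, with a statement that it is confounded by treatment choice. In section 8.1, define the safety set as all patients who received at least one capsule or other study treatment.

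The cost is extra tables from data already collected, with no change to visits, treatment or sample size. The all-cause capsule rate will be at least as high as the device-related rate, which will still be shown beside it.
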